Important Medical Event Requiring Medical or Surgical Intervention to Prevent Serious Outcome	An important medical event that may not be immediately life-threatening or result in death or hospitalization, but based on medical judgment may jeopardize the subject and may require medical or surgical intervention to prevent any of the outcomes listed above (i.e., death of subject, life threatening, hospitalization, prolongation of hospitalization, congenital anomaly, or persistent or significant disability/incapacity). Additionally, any elective or spontaneous abortion or stillbirth is considered an important medical event. Examples of such events include allergic bronchospasm requiring intensive treatment in an emergency room or at home, blood dyscrasias or convulsions that do not result in inpatient hospitalization, or the development of drug dependency or drug abuse.

All adverse events reported from the time of study drug administration until 12 weeks after the last injection will be collected, whether solicited or spontaneously reported by the subject. Subjects who discontinue study drug treatment but continue to participate in the study will have AEs collected for the remainder of study participation. In addition, serious adverse events and protocol-related non-serious adverse events will be collected from the time the subject signs the study-specific informed consent.

Additionally, in order to assist the adjudication process, additional information on any potential major adverse cardiovascular events will be collected, if applicable.

AbbVie will be responsible for Suspected Unexpected Serious Adverse Reactions (SUSAR) reporting for the Investigational Medicinal Product (IMP) in accordance with global and local requirements.

Adverse events will be monitored throughout the study to identify any of special interest that may indicate a trend or risk to subjects.

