## Recording Data and Analyses of Safety Findings

Adverse events will be coded using the Medical Dictionary for Regulatory Activities (MedDRA). The number and percentage of subjects with treatment-emergent adverse events (i.e., any event that begins or worsens in severity after initiation of study drug through 12 weeks after the last injection) will be tabulated by primary MedDRA System Organ Class (SOC) and preferred term (PT). The tabulation of the number of subjects with treatment emergent adverse events by severity grade and relationship to study drug also will be provided. Subjects reporting more than 1 adverse event for a given MedDRA preferred term will be counted only once for that term using the most severe grade according to the severity grade table and the most related according to the relationship to study drug tables. Subjects reporting more than 1 type of event within an SOC will be counted only once for that SOC.

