## 7.4 Statistical Analyses for Safety

---

The safety analyses will be carried out using the Safety Population and will be based on treatments the subjects actually received. Safety will be assessed by AEs, physical examination, laboratory assessments, and vital signs. Note that missing safety data will not be imputed. Analysis details will be specified in the SAP.

Adverse events will be coded using MedDRA. Treatment-emergent AEs (TEAEs) are defined as those that began or worsened in severity after the first dose of study drug and no more than 5 half-lives of the drug after the last dose of study drug. Specifically, 30 days will be used for upadacitinib, and 84 days (12 weeks) will be used for dupilumab. The number and percentage of subjects experiencing TEAEs will be tabulated using the MedDRA SOC and preferred term (PT), by severity, and by relationship to the study drug as assessed by the investigator. Summaries (including percentages and events per 100 patient-years) of SAEs, deaths, AEs leading to discontinuation and AESIs will be provided as well. Pre-treatment AEs will be summarized separately.

For laboratory and vital signs, mean change from Baseline and percentage of subject with evaluations meeting criteria for pre-defined Potentially Clinically Significant values will be summarized.

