9.2 Adverse Events

9.2.1 Treatment-Emergent Adverse Events

Treatment-emergent adverse events (TEAEs) are defined as any adverse events that begin or worsen in severity after initiation of upadacitinib/dupilumab through 30 days following the last dose of upadacitinib or 84 days following the last dose of dupilumab, regardless of any study drug interruption. If a missing or an incomplete onset date is collected for an adverse event, the event will be assumed to be treatment-emergent unless there is other evidence that confirms that the event is not treatment-emergent (e.g., the event end date is prior to the study drug start date).

Pre-treatment AEs are defined as AEs that occurred before the first dose of upadacitinib/dupilumab. Post-treatment AEs are defined as AEs that occurred beyond 30 days after the last dose of upadacitinib or 84 days after the last dose of dupilumab.

Adverse event data will be coded using the Medical Dictionary for Drug Regulatory Activities (MedDRA) version 22.1 or most up to date version.

Summary tables will be presented as follows:

1. Adverse Event Overview

An overview of AEs will be presented consisting of the number and percentage of subjects experiencing at least one event for each of the following AE categories 1) from Baseline to Week 16 visit and 2) the entire treatment period, respectively:

- Any treatment-emergent AE
- Any treatment-emergent AE related to study drug according to the investigator
- Any severe treatment-emergent AE (Grade 3 and above according to NCI CTCAE version 5.0)
- Any serious treatment-emergent AE (SAE)
- Any treatment-emergent AE leading to discontinuation of study drug
- Any treatment-emergent AE leading to death
- AEs of Special Interest
- Other Safety Topics of Interest
- Any treatment-emergent SAE related to study drug according to the investigator
- Any TEAE leading to death
- All deaths
 - Deaths occurring \leq 30 days after last dose of upadacitinib or \leq 84 days after last dose of dupilumab
 - Deaths occurring $>$ 30 days after last dose of upadacitinib and $>$ 84 days after last dose of dupilumab

2. Treatment-Emergent Adverse Events by System Organ Class and Preferred Term

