- Any TEAE leading to discontinuations of study drug
- Any severe TEAE
- Any TEAE related to study drug according to the investigator
- Any treatment-emergent SAE related to study drug according to the investigator
- Any TEAE leading to death
- TEAEs of Special Interest
- Other Safety Topics of Interest

Additional AEs may be considered for tabulation/summary based on recommendations from Clinical and Safety as deemed appropriate.

AEs per 100 patient-years of exposure is defined as the number of AEs divided by the total exposure in 100 patient-years. Note that one event per preferred term per day per subject will be counted in the calculation of the number of AEs (i.e., a preferred term will

not be counted twice on the same day for the same subject). See the calculation method below:

$$100 * (\text{Number of TEAEs}) / (\text{Total Patient Years})$$

where total patient years is defined as the sum of the study drug duration (defined in Section 6.0) of all subjects normalized by 365.25, and rounded to 1 decimal place.

6. Treatment-Emergent Adverse Events Rates per 100 Patient-Years of Study Drug Exposure by SOC and PT

For each treatment group, the TEAE rate per 100 patient-years of exposure will be calculated overall, for each SOC and each PT, for each of the following events:

- All TEAEs
- Treatment-emergent serious adverse events
- Treatment-emergent severe adverse events
- TEAEs related to study drug according to the investigator
- TEAEs leading to discontinuation of study drug
- TEAE leading to death

7. Listing of Adverse Events

The following additional summaries will be provided for treatment-emergent adverse events, unless otherwise specified.

- List of subject numbers associated with each PT for TEAEs.
- List of subject numbers associated with each PT for -TEAEs related to study drug according to the investigator Listing of pretreatment AEs.
- Listing of treatment-emergent SAEs.
- Listing of TEAEs leading to discontinuation of study drug.
- Listing of all deaths.
- Listing of treatment-emergent AESIs.

- Listings of other safety topics of interest
- Listings of pre-treatment AEs.

8. Acne Adverse Events

The investigator-identified acne AEs will be summarized by involvement, morphology, and acne risk factors.

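### The protocol has two treatment-emergent windows for upadacitinib, and under the SAP's shorter one late non-fatal SAEs outside the special-interest list have no planned output

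*SAP*

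**What the plan says.** **Collection.** Protocol Section 6.1 sets one rule for both arms: "All adverse events reported from the time of study drug administration until 12 weeks after the last injection will be collected". It goes further for subjects who stop drug but stay: "Subjects who discontinue study drug treatment but continue to participate in the study will have AEs collected for the remainder of study participation".

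**Definition of treatment-emergent.** The protocol gives two.
- Section 6.1, under the recording and analysis of safety findings: "any event that begins or worsens in severity after initiation of study drug through 12 weeks after the last injection". No distinction is made between arms.
- Section 7.4, which invokes five half-lives: "Specifically, 30 days will be used for upadacitinib, and 84 days (12 weeks) will be used for dupilumab".

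SAP Section 9.2.1 follows Section 7.4: "through 30 days following the last dose of upadacitinib or 84 days following the last dose of dupilumab".

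**Output.** SAP Section 9.2.1 also defines a pre-treatment and a post-treatment class. Pre-treatment events receive a listing. The post-treatment class ("Post-treatment AEs are defined as AEs that occurred beyond 30 days after the last dose of upadacitinib", with the 84-day counterpart for dupilumab) is not mentioned again. The SAE listing is "Listing of treatment-emergent SAEs", and the item 7 listing of events of special interest carries the same restriction. Deaths are the exception: the overview table has a row for deaths beyond the 30-day and 84-day limits, and there is a "Listing of all deaths".

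**The concern.** The study's objective covers safety as well as efficacy against dupilumab. Two problems follow from the text.

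First, the upadacitinib treatment-emergent count depends on which protocol section is applied, because an event 31 or more days after the last tablet can be inside the Section 6.1 window and outside the Section 7.4 window.

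Second, under the SAP rule a non-fatal SAE in that interval on upadacitinib is collected and then assigned to no table or listing, unless it happens to be an event of special interest. The corresponding event on dupilumab, up to 84 days after the last injection, is tabulated. The SAP treats late fatal events as reportable but makes no provision for late non-fatal serious ones, and the gap falls mainly on the investigational arm.

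**Working it through.** **Inputs from the documents**
- Last injection (placebo in the upadacitinib arm): Week 22, so 22 × 7 + 1 = Day 155 (Protocol 4.1).
- Last tablet: up to the Week 24 visit, so Day 168 or 169 (Protocol 4.1).
- Collection ends 84 days after the last injection; 12 × 7 = 84, as Protocol 7.4 states.
- SAP window: last upadacitinib dose + 30 days, or last dupilumab dose + 84 days.
- The 12-week follow-up visit applies to subjects who do not enter the open-label study. Their number is not given.

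**Completer not entering the open-label study**
- Collection ends: 155 + 84 = Day 239.
- Upadacitinib window ends: 168 + 30 = Day 198, or 169 + 30 = Day 199.
- Uncovered: 239 − 198 = 41 days, or 239 − 199 = 40 days. That is 41 of 71, or 40 of 70, collected days after the last tablet (57% to 58%).
- Dupilumab: window and collection both end at 155 + 84 = Day 239, so 0 days.
- In general, for upadacitinib, uncovered days = (84 − 30) − (days from last injection to last tablet). If both fall on the same day this is 54.

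**Subject stopping both treatments at Week 4 (Day 29) and followed to Week 24 (Day 169)**
- Upadacitinib: window ends 29 + 30 = Day 59; uncovered 169 − 59 = 110 days.
- Dupilumab: window ends 29 + 84 = Day 113; uncovered 169 − 113 = 56 days.
- One-sided part: 110 − 56 = 54 days. The other 56 days are uncovered in both arms and are treatment-emergent under neither protocol definition.

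**Person-time in the upadacitinib arm (assumed shares; N = 325)**
- No early stoppers, 10% to 30% not rolling over (33 to 98 subjects): 33 × 41 / 365.25 = 3.7 and 98 × 41 / 365.25 = 11.0 person-years.
- Adding 30 assumed Week 4 stoppers, one-sided part only: 30 × 54 / 365.25 = 4.4, giving 8.1 to 15.4 person-years.
- Wider range, with 5% to 100% of the arm having the follow-up at 40 days each: 325 × 0.05 × 40 / 365.25 = 1.8 to 325 × 40 / 365.25 = 35.6 person-years.
- At an assumed 6 SAEs per 100 person-years, 3.7 to 15.4 person-years correspond to about 0.2 to 0.9 SAE.

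**Which outputs could show a late non-fatal event (SAP 9.2.1 to 9.2.3, Appendix B)**
- Tables by organ class and preferred term, by toxicity and by frequency, and the rate tables: treatment-emergent. The rate overview opens by referring to the whole study, but the numerator in its formula is TEAEs.
- Item 7 listings: treatment-emergent unless stated otherwise. The SAE and special-interest listings say so expressly.
- Overview rows for events of special interest and other safety topics: no treatment-emergent label.
- Sections 9.2.2 and 9.2.3: tables for Baseline to Week 16 and for the entire treatment period, plus tabular listings, with no treatment-emergent label.
- Adjudicated cardiovascular and thrombotic events: taken from the adjudication committee's output, with no window stated.

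So a late SAE outside the special-interest and other-safety-topic definitions has no route into any planned output. For a late event of special interest the text does not settle the matter.

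**The case against.** The strongest reply is that the 30-day and 84-day limits are deliberate. Protocol 7.4 ties them to five half-lives, and the SAP version history says the definition was clarified to reflect the active drugs' safety more accurately. That stands: the asymmetric window is a defensible choice for the main tables. It does not explain why the class left outside it has no output, or why Section 6.1 says something else.

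A reader might go further and infer that every adverse event table is restricted to treatment-emergent events, so that a late malignancy or thrombosis on upadacitinib would never be shown. The documents do not support that. Both are events of special interest, and several of those outputs carry no such label. The reference to the entire treatment period does not exclude late events either, because the TEAE tables use the same phrase and still count events 30 or 84 days after dosing.

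A reader might also treat all 110 uncovered days of a Week 4 stopper as a loss in one arm. Only 54 are.

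Two mitigations are weaker. SAP 9.2.1 allows extra tabulations on clinical or safety advice, but these are optional. Protocol 7.4 promises SAE summaries without the treatment-emergent label, but it leaves the details to the SAP, which restricts them. Finally, SAEs are still reported within 24 hours and the monitoring committee sees unblinded safety data, so subject protection during the trial is unaffected. The point concerns the report.

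**Conclusion.** The concern holds in a limited form. Protocol 6.1 and 7.4 conflict on the upadacitinib window. Under the rule the SAP adopts, late non-fatal SAEs outside the special-interest list are collected without any planned output, and coverage of late events of special interest is unclear. The day counts (40 to 41 against 0 for completers outside the extension; 54 one-sided days for a Week 4 stopper followed to Week 24) follow from the documents' own schedule.

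The person-year figures do not. They rest on assumed rollover, an assumed 30 early stoppers who all stop at Week 4 and all stay to Week 24 (staying is only encouraged), and an assumed SAE rate. On those figures the expected loss is at most about one SAE. The primary endpoint and type I error are not affected. The change should still be made, because even one such event ought to be traceable in a trial whose objective includes safety.

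**What to change.** 1. Reconcile Protocol 6.1 with Protocol 7.4 so that one definition governs the TEAE tables.
2. In SAP 9.2.1, add a listing by arm of post-treatment SAEs and events of special interest, from the end of the treatment-emergent window to the end of follow-up in this study.
3. Add one supplementary by-arm summary of SAEs and events of special interest over a common window, from first dose through 12 weeks after the last injection (active or placebo), with person-time at risk. A count table starting where each arm's own window ends should be avoided: it would give upadacitinib completers about 41 days and dupilumab completers 0 by construction.
4. State which window applies to the outputs for events of special interest, other safety topics and adjudicated events in SAP 9.2.1 to 9.2.3 and Appendix B.

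The cost is one listing, one supplementary table and wording corrections in the two documents. No new data are needed, and the 30-day and 84-day windows can stay for the main tables if that is the definition chosen under item 1.

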## Severe (Grade 3 - 5)

Grade 3	Severe or medically significant but not immediately life-threatening; hospitalization or prolongation of hospitalization indicated; disabling; limiting self care ADL (Self care ADL refers to bathing, dressing and undressing, feeding self, using the toilet, taking medications, and not bedridden)
Grade 4	Life-threatening consequences; urgent intervention indicated
Grade 5	Death related to AE

The investigator will use the following definitions to assess the relationship of the AE to the use of study drug:

**Reasonable Possibility** – After consideration of factors including timing of the event, biologic plausibility, clinical judgment, and potential alternative causes, there is sufficient evidence (information) to suggest a causal relationship.

**No Reasonable Possibility** – After consideration of factors including timing of the event, biologic plausibility, clinical judgment, and potential alternative causes, there is insufficient evidence (information) to suggest a causal relationship.

For causality assessments, events assessed as having a reasonable possibility of being related to the study drug will be considered "associated." Events assessed as having no reasonable possibility of being related to study drug will be considered "not associated." In addition, when the investigator has not reported a causality or deemed it not assessable, AbbVie will consider the event associated.

If an investigator's opinion of no reasonable possibility of being related to study drug is given, an Other cause of event must be provided by the investigator for the SAE.

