TEAEs will be summarized and presented using primary MedDRA version 22.1 or later by system organ class (SOC) and preferred terms (PT) 1) from Baseline to Week 16 visit and 2) the entire treatment period, respectively. The SOCs will be presented in alphabetical order, and the PTs will be presented in alphabetical order within each SOC. Subjects reporting more than one adverse event for a given MedDRA preferred term will be counted only once for that term (most severe incident for the severity tables and most related incident for the relationship tables). A subject who reports more than 1 AE in different SOCs will be counted only once in the overall total. Subjects reporting more than one type of adverse event will be counted only once in the overall total.

The following summaries of adverse events will be generated:

- All TEAEs
- Treatment-emergent serious adverse events
- Treatment-emergent severe adverse events
- TEAEs related to study drug according to the investigator
- TEAEs leading to discontinuation of study drug
- TEAE leading to death

3. Treatment-Emergent Adverse Events by Maximum Toxicity

The severity grading of AEs follows the NCI CTCAE version 5.0.

TEAEs will be summarized by maximum toxicity. For summaries of AEs by toxicity, each subject is counted only once – according to the maximum toxicity level observed. If a subject has an AE with an unknown toxicity, then the subject will be counted in the toxicity category of "unknown." The only exception is that if the subject has another occurrence of the same AE with the most extreme, non-fatal NCI CTCAE toxicity (i.e., grade 4) or is fatal (grade 5). In this case, the subject will be counted under grade 4 if

non-fatal or 5 if fatal. For tables that look at severity instead of toxicity, the subjects that have an unknown NCI CTCAE grade but another occurrence of the same AE that is considered severe (grade ≥ 3) will be counted under severe.

4. Treatment-Emergent Adverse Events by Preferred Term in Decreasing Frequency

TEAEs occurring in either treatment groups will be summarized by MedDRA PT in decreasing frequency of upadacitinib, respectively.

5. Overview of Adverse Events by 100 Patient Years

AEs occurring during the entire study will be presented by event rate per 100 patient years. These will be presented by treatment group for the following AE categories 1) from Baseline to Week 16 visit and 2) the entire treatment period, respectively.

- Any TEAE
- Any treatment-emergent SAE

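### In SAP 9.2.1 item 3, an ungraded AE can move a subject with a known Grade 3 or higher event into the unknown column, so the maximum-toxicity table may not reconcile with the severe-TEAE and death lines

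*SAP*

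**What the plan says.** SAP 9.2.1 item 3 (TEAEs by maximum toxicity) opens with a general principle: "each subject is counted only once – according to the maximum toxicity level observed". It then deals with missing grades: "If a subject has an AE with an unknown toxicity, then the subject will be counted in the toxicity category of" *unknown*. One exception follows: "The only exception is that if the subject has another occurrence of the same AE with the most extreme, non-fatal NCI CTCAE toxicity", meaning Grade 4, or a fatal (Grade 5) occurrence. Such a subject is shown at Grade 4 or 5. Grade 3 is not covered, and the exception is tied to the same AE.

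The same paragraph gives severity tables a separate rule. It begins "For tables that look at severity instead of toxicity, the subjects that have an unknown NCI CTCAE grade" and provides that a subject with "another occurrence of the same AE that is considered severe (grade ≥ 3) will be counted under severe". SAP 9.2.1 item 2 keeps, per preferred term, the "most severe incident for the severity tables and most related incident for the relationship tables".

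Protocol 6.1 (Recording Data and Analyses of Safety Findings) plans a tabulation by severity grade in which a subject with repeated events of one term "will be counted only once for that term using the most severe grade according to the severity grade table". It says nothing about ungraded events. Protocol 6.1 also asks investigators to grade every AE, gives a generic scale for events that CTCAE does not cover, and defines "Severe (Grade 3 - 5") as the top severity category.

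The SAP 9.2.1 overview (item 1) counts subjects with at least one severe TEAE, Grade 3 and above, and subjects with a TEAE leading to death. Neither line has an unknown-grade exception.

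**The concern.** A recorded Grade 3 is a certain lower bound on a subject's maximum grade. Item 3 removes it from the graded columns because another event has no grade. Among subjects with a known Grade 3 or higher event, the rule works in one direction: it can take them out of the Grade 3 to 5 columns but cannot put them in.

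The scope of the rule is also unclear. The exception refers to the same AE, which makes sense in a preferred-term row. Item 3 does not say how it works in an SOC row or the any-AE row, where events of different terms are pooled.

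At stake is whether the descriptive safety tables agree with each other. A reader who adds Grades 3 to 5 in the maximum-toxicity table may get fewer subjects than the overview reports as severe, with no explanation in the output. Type I error, power and the primary endpoint are not affected.

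**Working it through.** The documents give no figure on this point, so there is none to reproduce. The check has two parts.

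**1. Apply each rule to two occurrences of the same preferred term, one of them ungraded**

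| Known grade + ungraded | SAP toxicity table | SAP severity table | Most severe recorded grade (Protocol 6.1 wording) |
|---|---|---|---|
| 1 | unknown | no specific rule | 1 |
| 2 | unknown | no specific rule | 2 |
| 3 | unknown | severe | 3 |
| 4 | 4 | severe | 4 |
| 5 | 5 | severe | 5 |

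Within a term, Grade 3 plus ungraded is the one combination in which the toxicity table's Grade 3 to 5 total and the severity table's severe count disagree.

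Next, ask what the ungraded event could change. With a known Grade 3, the non-fatal maximum could be 3 or 4, so the exact grade is undetermined, but the severity category can only be severe. With a known Grade 4, the non-fatal maximum can only be 4.

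**Different terms.** Take a subject with an ungraded minor event of term A and a fatal event of term B. In the any-AE row the fatal event is not another occurrence of the ungraded AE, so on a literal reading the exception does not apply and the subject is *unknown*. The overview still counts the same subject as having a severe TEAE and a TEAE leading to death.

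**2. Size, per arm of 325 (planned size, SAP 2.4)**

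The documents give neither a rate of ungraded AEs nor an expected rate of Grade 3 or higher events. All rates below are assumptions.

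*Any-AE row, literal reading.* Subjects moved = 325 × P × [1 − (1 − q)^m], where P is the share of subjects with a Grade 3 or higher event, q the chance that an AE is ungraded, and m the number of other AEs in such a subject. Ungraded events are taken as independent.

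- Low: P = 0.05, q = 0.002, m = 2. 325 × 0.05 = 16.25; 1 − 0.998² = 0.0040; product 0.06.
- High: P = 0.10, q = 0.02, m = 4. 325 × 0.10 = 32.5; 1 − 0.98⁴ = 0.0776; product 2.5.

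This slightly overstates the effect, because it ignores the exemption for a Grade 4 or 5 occurrence of the same AE. With q = 0 the result is 0.

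*Same-term conflict only.* Subjects moved = 325 × (share with Grade 3) × (share of those with an ungraded occurrence of the same term).

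- Grade 3 in 3% to 8% of subjects is 9.75 to 26 subjects.
- With 0% to 10% of them having an ungraded repeat, 0 to 26 × 0.10 = 2.6 subjects move.
- The 10% is generous. If each had one repeat of the term, ungraded with probability 0.002 to 0.02 as above, the range is 9.75 × 0.002 = 0.02 to 26 × 0.02 = 0.5.

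**The case against.** The best defence is that, within one preferred term, the two SAP rules follow a single principle: keep the known grade only when the ungraded occurrence could not raise the category. Severe is the top severity category, so a known Grade 3 settles it. Grade 3 is not the top toxicity grade, so *unknown* describes the maximum honestly. The SAP also separates the two table types expressly. This stands. A reader might infer that the SAP contradicts itself here, but the documents do not support that.

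A reader might also infer a direct contradiction with the protocol. That is too strong. Protocol 6.1 does not say what to do with an ungraded event, Protocol 7.4 leaves analysis details to the SAP, and SAP item 2 follows the most-severe principle for severity tables. What remains is a departure in one table, for a case the protocol leaves open. SAP 1.0 refers to Section 12.0 for changes from the protocol's analyses, and Section 12.0 does not name this one; it records only that safety-analysis details were added.

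A third possible inference is that Grade 3 counts differ between tables. The severity tables report severe (Grade 3 or higher), so there is no second Grade 3 count to compare. Any mismatch also requires ungraded AEs, which Protocol 6.1 is meant to prevent.

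Severe events are not lost from the report either. They remain in the overview, the severe-TEAE summary by SOC and preferred term, and the rates per 100 patient-years.

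The defence does not cover rows that pool different terms. Nothing can exceed a Grade 5 event, yet the literal text still sends that subject to *unknown*. Even within a term, *unknown* sits poorly with a table defined by the maximum level observed, because an ungraded event supplies no observed level.

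**Conclusion.** The point holds as a gap in scope and reconciliation for one descriptive table. If any AEs are ungraded, the Grade 3-or-higher total in the maximum-toxicity table can fall below the severe-TEAE line. On the literal reading of the any-AE row, its Grade 5 count can also fall below the line for TEAEs leading to death. The table then departs from the most-severe-grade tabulation in Protocol 6.1.

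The size is about 0 to 2.5 subjects per arm in the any-AE row, and probably less for the same-term conflict alone. These figures rest wholly on assumed rates of ungraded AEs, of Grade 3 or higher events and of other AEs per subject. If every AE is graded, the tables agree exactly. This is a minor clarification to make before the tables are programmed.

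**What to change.** Replace the unknown-grade sentences for the toxicity table in SAP 9.2.1 item 3 with a rule stated per row: in each preferred-term, SOC and overall row, count the subject at the highest known grade among the events in that row, and use *unknown* only when no event in the row has a grade. Add a footnote giving the number of subjects with an ungraded event and noting that their true maximum may be higher.

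Within a term, Grade 3 plus ungraded then moves from *unknown* to Grade 3, and Grades 3 to 5 add up to the severe count. Grade 1 or 2 plus ungraded moves to Grade 1 or 2. Grade 4 or 5 plus ungraded is unchanged. In the overall row, the Grade 3-or-higher total matches the overview's severe-TEAE line.

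The cost is a sentence or two in the SAP and a small programming change. The trade-off is that a subject whose ungraded event was in truth worse is shown at the known grade; the footnote makes that visible.
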